## 2. Study Objectives

### 2.1 Study 1

Study 1 will test the central hypothesis that high dose isoflurane anesthesia inducing EEG burst suppression (High ISO/BS+) is a more effective intervention for severe depression when compared to a low dose isoflurane anesthesia that does not induce EEG burst suppression (Low ISO/BS-). The proposed study is a randomized, double-blind trial that will evaluate 30 actively depressed participants with moderate to severe depression. Depression outcomes will be compared between two groups of participants (n=15 per group) who have received 10 treatment applications over a period of three weeks of either High ISO/BS+ or Low ISO/BS-.

Aim 1. To determine whether High ISO/BS+ is more effective than Low ISO/BS- in producing either a treatment response (defined as 50% reduction in depression scores) or full remission of depressive symptoms. We hypothesize that significantly more depressed participants randomized to receive 10 treatments of High ISO/BS+ compared to Low ISO/BS- will show a positive treatment response or full remission by treatment end. Based on the STAR\*D Trial, a responder is a participant showing 50% reduction in depression score and full remission is defined as a score of 0-10 on the HRSD-24 scale and score of 0-5 on the QIDS-SR16.

Aim 2. Preliminary data on neural and immune pathways that are differentially affected by the 2 treatments and associated with antidepressant effects will be explored by comparing changes from pre-treatment to post-treatment in full transcriptome leukocyte gene expression (using the RNA Seq method).

Aim 3. To measure the central neurochemical effects of isoflurane treatment, we will quantify neurotransmitter levels (GABA and glutamate) using magnetic resonance spectroscopy.

### 2.2 Pilot Study 2

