Study 2 is designed to complement Study 1 in providing additional support for the hypothesis that burst suppression is an important mechanism for antidepressant treatment effects of anesthesia in moderate to severe depression. If Study 1 demonstrates that more participants receiving High ISO/BS+ undergo remission than those receiving Low ISO/BS-, this could be interpreted as a dose response effect for isoflurane that is not specifically a result of burst suppression. Demonstrating that a different anesthetic administered at doses producing 80% burst suppression for 10 treatment session is also effective in producing depression remission would add support for the hypothesis that the underlying mechanism is burst suppression. Therefore, Study 2 will be an open-label trial to provide preliminary data that propofol, an intravenous anesthetic with a favorable safety profile, administered for 10 treatment sessions at levels to induce 80% burst suppression, also is effective in producing depression remission in 50% or more of the pilot sample of 10 depressed participants.

Aim 4. To determine whether propofol anesthesia at a level to produce 80% EEG burst suppression is effective in producing remission of depressive symptoms. We hypothesize that

the majority of depressed participants (n=10) receiving 10 treatments of propofol anesthesia will achieve remission of symptoms by treatment end.

Aim 5. Preliminary data on neural and immune pathways that are differentially affected by the 2 treatments and associated with antidepressant effects will be explored using full transcriptome leukocyte gene expression (RNA Seq).

Aim 6. To measure the central neurochemical effects of propofol treatment, we will quantify neurotransmitter levels (GABA and glutamate) using magnetic resonance spectroscopy.

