If evidence from these studies support deep anesthesia with BS+ (High ISO/BS+ and/or propofol/BS+), it would point to a possible mechanism of action for the antidepressant effects of deep anesthesia. Treatments that evoke burst suppression, in theory, could have all the benefits of ECT without the neurocognitive deficits and the associated social stigma.

As detailed above, even in the minority of cases when initial pharmacological treatment for depression is effective, it usually requires months before symptoms show satisfactory remission, and during that time patients and physicians have no objective test to use to verify that the intervention is or is not likely to be successful. Even with ECT, where improvement can be noted in days rather than weeks or months, initial signs of improvement are based on relatively soft non-objective measures such as global improvement that rely heavily on the physician's individual clinical insight and experience. Thus, there is a great need to establish convenient, reliable and objective biomarkers for treatment-induced changes that reliably predict clinical improvement in cases of depression.

By comparing changes in full transcriptome leukocyte gene expression from pre- to post-treatment in these 40 participants treated with High ISO/BS+ vs. Low ISO/BS-, and propofol/BS+, this investigation will explore the neural and immune pathways through which anesthetic-induced antidepressant effects are produced, and will be able to identify candidate neural pathways that can later be reconfirmed in larger samples. In particular, we will examine the possible role of NMDA receptor subunits, GABA-ergic and ATP-responsive ion channel

pathways as well as other putative depression- or suicidality-linked neuroimmune pathways previously associated with refractory depression or suicidality by our group and others.

Burst suppression anesthesia is thought to strongly engage the brain's major inhibitory and excitatory neurotransmitter systems, GABA and glutamate, respectively. Indeed, both isoflurane and propofol are thought to directly bind GABA and glutamate receptors. To better understand the brain mechanisms through which burst suppression causes antidepressant effects, we will measure GABA and glutamate concentrations in vivo using magnetic resonance spectroscopy, a type of MRI.

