## **7. Statistical Considerations**

Statistical analyses will employ a statistical mediation model framework. Any participant missing necessary information will be excluded from statistical analysis. Only participants with usable data will be included in the analyses. If the original statistical plan becomes infeasible, the original plan and the modifications made will be reported.

**7.1 Aim 1.** To determine if significantly more depressed participants randomized to receive 10 treatments of High ISO/BS+ will show a positive treatment response (defined as 50% reduction in depression scores) or achieve full remission of symptoms by treatment end compared to those in the Low ISO/BS-group, odds of treatment response and remission will be compared between groups using logistic regression analysis with positive response at treatment end (yes/no) as the dependent variable, and treatment group (High ISO/BS+ vs Low ISO/BS-) as the independent variable. Positive treatment response is defined as 50% reduction in depression scores, and remission will be defined as a score of 0-10 on the HRSD-24 scale.

Covariates will include baseline depression severity and possibly other baseline demographic and clinical measures as needed.

**7.2 Aims 2 and 5.** Using RNA SEQ methods, we will also explore whether participants who respond to treatment show blood-based changes in gene expression of neural and immune pathways previously associated with refractory depression or suicidality by our group or others. A t-test or non-parametric Wilcoxon test will be used, as appropriate. Change from baseline to end of treatment in gene expression levels will be correlated with change from baseline to end of treatment in HRSD-24.

**7.3 Aim 4.** In the open-label trial of propofol, initial evidence of efficacy will be defined by the percent of participants who show at least a 20% reduction in both HRSD and QIDS scores (initial improvement, as employed in the STAR D investigation) and who are propofol/BS+ responders (defined as 50% or more reduction in both HRSD-24 and QIDS scores). Secondary evidence of efficacy will be defined by comparing the percent of participants who are responders to propofol/BS+ vs. to the Low ISO/BS- control condition in the randomized trial.

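### Section 7.2 does not specify the randomised between-arm comparison of expression change that Aim 2 announces, and its response analyses carry no treatment term

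*Combined protocol and SAP*

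**What the plan says.** Section 2.1 (Aim 2) concerns "neural and immune pathways that are differentially affected by the 2 treatments and associated with antidepressant effects", to be explored by "comparing changes from pre-treatment to post-treatment in full transcriptome leukocyte gene expression". The Background (section 3) names the groups whose changes will be compared: "participants treated with High ISO/BS+ vs. Low ISO/BS-, and propofol/BS"+.

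Section 7.2 covers Aims 2 and 5 together and contains three elements:

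- a plan to "explore whether participants who respond to treatment show blood-based changes in gene expression of neural and immune pathways";
- a test: "A t-test or non-parametric Wilcoxon test will be used, as appropriate";
- an association: "Change from baseline to end of treatment in gene expression levels will be correlated with change from baseline to end of treatment in HRSD-24".

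Section 7 opens with a general statement: "Statistical analyses will employ a statistical mediation model framework". It does not name mediators, paths or models. Section 7.1, on the clinical outcome, does name treatment group as the independent variable.

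Aim 5 (section 2.2) repeats Aim 2's wording, "differentially affected by the 2 treatments and associated with antidepressant effects will be explored", although Study 2 is a single-arm, open-label pilot.

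**The concern.** Aim 2 joins two questions: does expression change differ between the randomised arms, and is it related to improvement? Section 7.2 gives an analysis only for the second.

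The second question is also exposed to confounding by arm. Response is observed after randomisation, and the trial's hypothesis is that it is more frequent on High ISO/BS+. Responders would then come disproportionately from the high-dose arm. A gene that reacts to anaesthetic depth, and has nothing to do with mood, would differ between responders and non-responders and would correlate with HRSD-24 change.

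The trial is about mechanism, and the Background intends candidate pathways to be taken into larger samples. A marker of dose mistaken for a marker of antidepressant effect would misdirect that work.

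**Working it through.** **1. The text, side by side.**

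| Place | Comparison by arm? | Relation to response? |
|---|---|---|
| Aim 2, section 2.1 | Yes, between the two treatments | Yes |
| Background, section 3 | Yes, three groups named | Yes, as biomarkers of improvement |
| Section 7, opening | Implied by mediation, not written out | Implied |
| Section 7.1 (Aim 1) | Yes, treatment group in the model | Not applicable |
| Section 7.2 (Aims 2 and 5) | Not stated; test groups unnamed | Yes, without a treatment term |

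The documents give no alpha, power, effect size or SD for gene expression, so there is no stated figure to reproduce. What follows is illustration.

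**2. Inputs.** From the documents: 15 per arm (section 2.1) and 75% response on High ISO/BS+ in the group's earlier open-label study (section 3). Assumed: the Low ISO/BS- response rates, the 50% v 20% scenario, arm effects of 1 and 0.5 SD of expression change, and a single gene at two-sided alpha 0.05.

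**3. How much of an arm effect leaks into a responder comparison.** Let expression change depend on arm only, with response rates pH and pL and equal arms. The share of High ISO/BS+ participants is pH/(pH+pL) among responders and (1−pH)/(2−pH−pL) among non-responders. The expected responder-minus-non-responder difference, as a fraction of the arm effect, is the first share minus the second:

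- 75% v 25%: 0.75/1.00 − 0.25/1.00 = 0.50
- 75% v 35%: 0.75/1.10 − 0.25/0.90 = 0.68 − 0.28 = 0.40
- 50% v 20%: 0.50/0.70 − 0.50/1.30 = 0.71 − 0.38 = 0.33

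The fraction is zero if response is equal in the arms (75% v 75%). It rises to 0.66 at 75% v 10%.

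**4. How often that gives a significant result.** Simulation with at least 20,000 genes per scenario, arm-only effect, response independent of the gene within arm:

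| Response, High v Low | Responder test, 1 SD | Responder test, 0.5 SD | With arm in the model |
|---|---|---|---|
| 75% v 25% | 24% | 10% | about 5% |
| 75% v 35% | 17% | 9% | about 5% |
| 50% v 20% | 12% | 7% | about 5% |

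Over a wider range at 1 SD, the responder test flags the gene 10% of the time at 75% v 50% and 38% at 75% v 10%.

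**5. The comparison that is not specified.** With 15 v 15, a two-sample t-test between arms has about 75% power at 1 SD and 26% at 0.5 SD. The difference detectable with 80% power is 1.06 SD. The responder test is therefore not a substitute: it picks up the arm effect far less often and attaches the wrong label to it.

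**6. The HRSD-24 correlation.** With an arm effect d on expression change and h on HRSD-24 change (each in within-arm SD units) and no link within arm, the correlation ignoring arm is (dh/4)/√[(1+d²/4)(1+h²/4)]. It is non-zero whenever both effects are. The documents give no spread for HRSD-24 change, so I put no rate on it.

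**The case against.** A reader might infer that the randomised contrast is never analysed. The documents do not support that. Aim 2 and the Background both say that changes will be compared, and the Background names the groups. The t-test or Wilcoxon sentence leaves its groups open: it could be the between-arm test, responders against non-responders, or a paired test within responders. A conventional mediation model also contains a treatment-to-expression path and an expression-to-outcome path adjusted for treatment, which are the two pieces in question. Nor does section 7.2 say that arms will be pooled; that is inferred from the absence of an arm term. All of this stands. What remains is that the announced comparison is not specified where the analyses are set out, and the mediation paths are not written down.

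It would likewise be too strong to say that Aim 5 has no conceivable comparator, since the Background lists propofol beside the isoflurane groups. But its reference to two treatments does not fit a single-arm study, and participants choose which study to join (section 4.3), so any such comparison is non-randomised.

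The size depends on assumptions. At 0.5 SD the excess is small. A full transcriptome would call for a stricter threshold than 0.05: at an illustrative alpha of 0.001 and 1 SD, the responder signal falls to 0.6-1.7% and between-arm power to about 21%. The absolute rates shrink, though 0.6-1.7% is still 6 to 17 times the nominal 0.1%.

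Finally, the Background also wants biomarkers that predict improvement. An unadjusted association serves that purpose and is not an error in itself. Adjustment for arm matters when the finding is read as mechanism.

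**Conclusion.** The point holds as a gap in specification with a practical consequence. Section 7.2 should be changed, but nothing here threatens the trial's main result. The half of Aim 2 about differences between treatments has no stated analysis, the test groups are undefined, and the stated response analyses carry no arm term.

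Carried out as written, those analyses can label an arm-only gene as response-linked at about 2.4 to 4.8 times the nominal rate at 1 SD (12/5 to 24/5) and 1.4 to 2 times at 0.5 SD (7/5 to 10/5). These figures rest on the assumed effect sizes, response rates and single-gene alpha, and on response truly differing by arm; if it does not, the excess disappears. Aims 2 and 5 are described as preliminary and exploratory, which limits the weight of the point.

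**What to change.** In section 7.2:

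1. State as the first Aim 2 analysis the comparison of pre-to-post expression change between High ISO/BS+ and Low ISO/BS- in all randomised Study 1 participants with samples. Say which groups the t-test or Wilcoxon test compares, and whether it is paired or two-sample.
2. Include arm in the models relating expression change to response or HRSD-24 change, consistent with the mediation framework. Label any unadjusted association as predictive only.
3. For Aim 5, report within-group change for propofol, and label any comparison with the isoflurane arms as non-randomised.

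The cost is SAP wording and one model term (one degree of freedom). The blood samples are already scheduled (sections 1 and 4.5), so no added participants, visits or assays are needed. Between-arm power will be modest at 15 per arm, and lower after any multiplicity control, which the write-up should acknowledge.

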#### **4.5 Study Visits**

**Screening:** Patients who have been referred or have volunteered for the study will be screened in person or by phone to verify that inclusion and exclusion criteria have been met.

**Consent procedures:** Each patient will be given a full verbal explanation of the study procedures, including risks, benefits, and alternatives, and will be given a copy of the approved written consent form. The patients will be given the opportunity to review the consent form and to discuss any questions or concerns with their own psychiatrist, our study investigators, or others if necessary prior to beginning study treatment procedures.

**Baseline:** Prior to the first treatment, depression severity will be assessed via a psychiatric interview, including completion of the HRSD-24 and MoCA, which will also verify inclusion and exclusion criteria. Immediately before treatment 1, the participant will complete the QIDS and a blood sample will be obtained from the IV line.

**Randomization (Study 1 only):** Participants who meet study criteria will be randomly assigned in blocks of 4 to either high or low dose isoflurane (High ISO/BS+ vs. Low ISO/BS-). We anticipate up to 15 participants in each arm; this sample size was defined by our prior study in which 8 participants were adequate to show significant antidepressant effects.

**Leukocyte Gene Expression:** Although our study is designed with EEG burst suppression as our primary target mechanism, we acknowledge that its effects must be mediated via specific neural pathways. Thus, we will explore possible neural and immune pathways associated with the antidepressant effects of deep anesthesia. Changes in full transcriptome leukocyte gene expression from pre- to post-treatment will be assessed from blood samples drawn before the first treatment and within 48 hours of the final (10th) treatment. In particular, we will examine the possible role of GABA-ergic and ATP-responsive ion channel pathways as well as other putative depression- or suicidality-linked neuroimmune pathways. We will also evaluate other ATP-responsive ion channels (purinergic, acid sensing and transient vanilloid receptor) or other

genes including IL-10 and other cytokines, SAT1, PTEN, MARCKS and MAP3K3 previously associated with refractory depression or suicidality by our group and others. [42918](#)

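### Section 7.2 fixes neither the set of genes or pathways to be tested nor any false-discovery control for full-transcriptome RNA-Seq data

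*Combined protocol and SAP*

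**What the plan says.** Aim 2 (Section 2.1) describes the analysis as "comparing changes from pre-treatment to post-treatment in full transcriptome leukocyte gene expression (using the RNA Seq method"; Aim 5 (Section 2.2) uses the same assay for propofol. Both aims are declared exploratory: "Preliminary data on neural and immune pathways that are differentially affected by the 2 treatments and associated with antidepressant effects will be explored".

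Section 7.2 asks whether participants who respond show changes in "gene expression of neural and immune pathways previously associated with refractory depression or suicidality by our group or others". For this it says "A t-test or non-parametric Wilcoxon test will be used, as appropriate", and it adds a second set of tests: "Change from baseline to end of treatment in gene expression levels will be correlated with change from baseline to end of treatment in HRSD-24".

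The candidates are described elsewhere, and loosely. Section 4.5 refers to GABA-ergic and ATP-responsive ion channel pathways and to "genes including IL-10 and other cytokines, SAT1, PTEN, MARCKS and MAP3K3 previously associated with refractory depression or suicidality". Section 3 also mentions NMDA receptor subunits, which the Section 4.5 list omits. Section 3 states the intended use: the study "will be able to identify candidate neural pathways that can later be reconfirmed in larger samples".

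The text available for review gives no significance level, gene count, unit of testing, multiplicity rule or RNA-Seq count model for these data. Section 8 was not available. The contents list titles it Training and Resources, so it is an unlikely place for such a rule.

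**The concern.** A full-transcriptome assay can supply thousands of test variables from at most 40 participants. Section 7.2 narrows the question to previously implicated pathways but does not list or count them, and the descriptions in Sections 3 and 4.5 are open-ended. The set could therefore be settled after the data are seen, anywhere from five genes to the whole transcriptome, with nothing limiting the proportion of false leads.

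What is at stake is the quality of the candidate list. Section 3 expects it to guide later work in larger samples, so chance findings would use up that later effort. The clinical conclusions do not depend on it.

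**Working it through.** The plan gives no figure for this analysis, so there is none to reproduce. The check asks how many chance findings the stated method allows under different readings of its scope.

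**Inputs from the documents:** 15 participants per arm in Study 1 (Section 2.1); 10 in Study 2 (Section 2.2); five individually named genes, IL-10, SAT1, PTEN, MARCKS and MAP3K3 (Section 4.5).

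**Assumptions, because the documents are silent:** two-sided 0.05 per test; 50 or 200 genes for a candidate list; 15,000 to 20,000 genes for a wide scan; a standardized effect of 0.8 to 1.2 in truly changed genes; and a High versus Low isoflurane contrast with all 30 participants usable.

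**1. Chance findings if nothing truly changes.** The expected number is m × 0.05. The probability of at least one is 1 − 0.95^m if tests are independent.

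| Genes tested (m) | Expected chance findings per family | Probability of at least one |
|---|---|---|
| 5 | 0.25 | 1 − 0.95^5 = 23% |
| 50 | 2.5 | 1 − 0.95^50 = 92% |
| 200 | 10 | above 99.9% |
| 15,000 | 750 | practically 1 |
| 20,000 | 1,000 | practically 1 |

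The expected counts do not need independence; the probabilities do. The HRSD-24 correlations are a second family of the same size.

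**2. Share of flagged genes that are false.** With a proportion π truly changed, the expected share is approximately (1 − π) × 0.05 / [(1 − π) × 0.05 + π × power]. Power from the noncentral t distribution, 15 versus 15, is 56%, 75% and 89% at effects 0.8, 1.0 and 1.2. At effect 1.0:

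- π = 1%: 0.0495 / (0.0495 + 0.00753) = 87%
- π = 5%: 0.0475 / (0.0475 + 0.03765) = 56%
- π = 10%: 0.045 / (0.045 + 0.0753) = 37%
- π = 30%: 0.035 / (0.035 + 0.2259) = 13%

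The share reaches one half at π = 0.05 / (0.05 + power), which is 8.2%, 6.2% and 5.3% at the three effects.

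**3. What false-discovery control costs.** Solving the same expression for the cutoff that gives a 5% share, at effect 1.0 with a plain t-test:

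| π | Per-gene cutoff | Power per truly changed gene (75% at 0.05) |
|---|---|---|
| 5% | 0.0004 | 13% |
| 10% | 0.0014 | 24% |
| 30% | 0.012 | 53% |

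**4. Wilcoxon in the propofol group.** If change is tested within the 10 participants, the smallest two-sided exact signed-rank p is 2/2^10 = 0.00195. Benjamini-Hochberg at 5% can flag a gene at that floor only if k ≥ 0.00195 × m / 0.05 genes reach it together: 1 of 5, 2 of 50, 8 of 200, 586 of 15,000 or 782 of 20,000.

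**The case against.** The strongest reply is that Section 7.2 does not describe a transcriptome-wide scan at all. A reader might infer one from the assay, but the sentence before the named tests confines the question to previously implicated pathways, and the unit of testing (gene, gene set or pathway) is not stated. That stands: testing every gene one by one is an inference. What it leaves untouched is that the narrower set is never closed.

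A reader might also infer that most flagged genes would be false. The documents do not support this, because they give neither the proportion truly changed nor the power. On the assumed inputs, it holds only below about 5-8% truly changed. That is plausible for a wide scan and less so for a short list chosen on earlier evidence.

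Three further objections stand:

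- Response and HRSD-24 change are closely related outcomes in the same participants. The correlations double the number of tests, but their chance findings would overlap, so the number of distinct false leads need not double.
- The signed-rank floor does not rule out the propofol analysis. Section 7.2 specifies no such within-group test, a t-test remains allowed and has no such floor, and a short family can pass with one or two genes at the minimum. The floor matters only for a wide Wilcoxon scan.
- The aims are preliminary, and reconfirmation is foreseen. This limits the severity. It does not remove the need for a stated rule, because the list decides what is reconfirmed.

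**Conclusion.** The point holds in a limited form. For full-transcriptome data intended to yield candidate pathways, the plan neither closes the tested set nor states any false-discovery control. At an assumed 0.05 per test, the consequence ranges from minor (0.25 expected chance findings for the five named genes) to large (750 to 1,000 per family in a wide scan), and nothing in the plan determines where in that range the analysis will fall. Even 50 genes would give a 92% chance of at least one false finding, if tests are independent and none truly changes.

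The gene counts, the per-test level, the effect sizes and the proportion truly changed are all assumptions. The absence of a rule is read directly from the text. The change is worth making because it costs little, but neither the Aim 1 comparison nor the Aim 4 propofol assessment depends on it.

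**What to change.** Rewrite Section 7.2 as follows:

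- State the unit of testing and the contrast. List the candidates from Section 4.5 by gene or pathway: the named genes plus the cytokine, GABA-ergic and ATP-responsive channel families. Settle whether the NMDA receptor subunits in Section 3 belong. Treat the list as one prespecified family with its own Benjamini-Hochberg control.
- Analyse any wider scan with an RNA-Seq model that shares variance across genes (negative-binomial or moderated linear) on paired change, at a stated false-discovery rate of 5-10%, and label it hypothesis-generating.
- Apply the same control to the HRSD-24 correlations.
- Do not use a Wilcoxon test for a wide scan in the 10-participant propofol group.

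The cost is SAP wording and analysis code; no extra samples or visits are needed. The downside is that fewer genes will be reported as significant and power per gene will be lower, as step 3 of the working shows for a plain t-test. This is a reason to keep the candidate family short and separate from any wide scan.

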### **9.2 Potential Benefits**

There may be no direct benefits to participants who volunteer for this research, although evidence suggests that participants receiving High ISO/BS+ may realize a clinical benefit. Information obtained from this work may provide insight into the role of burst suppression as a possible mechanism underlying the anti-depressant effects of deep anesthesia. The gene expression analyses may in turn identify potential neuro-immune pathways associated with depression treatment.

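### Section 7.2 analyses change in leukocyte gene expression without accounting for change in leukocyte composition, so a composition shift, if one occurs, could be read as a within-cell pathway change

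*Combined protocol and SAP*

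**What the plan says.** Section 4.5 (Leukocyte Gene Expression) describes the material: "Changes in full transcriptome leukocyte gene expression from pre- to post-treatment will be assessed from blood samples drawn before the first treatment" and again within 48 hours of the tenth treatment. The objectives in section 2 give the purpose: "Preliminary data on neural and immune pathways that are differentially affected by the 2 treatments and associated with antidepressant effects will be explored".

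The analysis is in section 7.2. It will "explore whether participants who respond to treatment show blood-based changes in gene expression of neural and immune pathways", and "A t-test or non-parametric Wilcoxon test will be used, as appropriate". The association with outcome is one sentence: "Change from baseline to end of treatment in gene expression levels will be correlated with change from baseline to end of treatment in HRSD-24".

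The only covariates named in section 7 are in 7.1, for the Aim 1 logistic regression: "Covariates will include baseline depression severity and possibly other baseline demographic and clinical measures as needed". These are baseline measures and are not carried into 7.2. Section 7 opens by invoking a mediation framework but names no mediator. The Schedule of Activities lists only a blood sample at visits 1 and 10, and section 5.4 says the samples are for biomarkers. I found no mention of a differential count, cell sorting, deconvolution or a cell-composition sensitivity analysis. Section 8 (Training and Resources) was not in the text available to me, but its title makes it an unlikely place for one.

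Section 9.2 gives the intended reading: "The gene expression analyses may in turn identify potential neuro-immune pathways associated with depression treatment". Section 3 treats the results as candidates for confirmation in larger samples.

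**The concern.** RNA from mixed leukocytes is a weighted sum over cell types. If the balance of neutrophils and lymphocytes differs between the two draws, genes expressed more in one type than the other move with it, although expression inside each cell is unchanged. The first draw precedes all study anesthesia. The second follows ten sessions over three weeks. The documents do not say whether the mix changes over that interval, and the planned analysis could not tell.

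What is at stake is the interpretation of Aims 2 and 5. A signal produced by composition could be taken forward as a change in pathway activity. Confirmation in a larger sample would not expose this if the larger study also ignored composition.

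**Working it through.** The documents give no sample-size basis, effect size, error rate or cell-count figure for Aims 2 and 5, so there is no planned figure to reproduce. Both steps below use assumed inputs and show only what could happen.

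**Step 1. Shift in the measured level of one gene.** Assumptions: two cell types (neutrophils and lymphocytes), equal RNA per cell, fixed expression within each cell, and a gene expressed 10-fold more in one type. With neutrophil share f, the measured level is

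- neutrophil-enriched gene: 10f + (1 − f)
- lymphocyte-enriched gene: f + 10(1 − f)

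| Neutrophil share | Neutrophil gene | Lymphocyte gene |
|---|---|---|
| 60% (start) | 6.0 + 0.4 = 6.4 | 0.6 + 4.0 = 4.6 |
| 65% | 6.5 + 0.35 = 6.85; 6.85/6.4 = +7.0% | 0.65 + 3.5 = 4.15; 4.15/4.6 = −9.8% |
| 70% | 7.0 + 0.3 = 7.3; 7.3/6.4 = +14.1% | 0.7 + 3.0 = 3.7; 3.7/4.6 = −19.6% |

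At 70% the log2 changes are +0.19 and −0.31. These are shifts in level. They bear on a pre-post comparison, and on a between-arm comparison if the arms shift differently. They do not by themselves show a false correlation with HRSD-24.

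**Step 2. Effect on the HRSD-24 correlation.** This was simulated with 4,000 runs per setting and within-cell expression held fixed. Assumptions: a cell type making up 30% of leukocytes, SD of change in its share 5 or 8 percentage points, 4- or 20-fold enrichment, log2 noise SD 0.2, and a Pearson correlation tested two-sided at 0.05 per gene. The sample is n = 30 (Study 1) or n = 40 (both studies).

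| Correlation of cell-share change with HRSD-24 change | Unadjusted rejection, n = 30 | Unadjusted rejection, n = 40 |
|---|---|---|
| 0 | about 5% | about 5% |
| 0.3 | 12–29% | 16–37% |
| 0.5 | 26–68% | 34–80% |

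Adjusting for the change in cell share brought the rate back to about 4.5–5.8% in every setting. That result takes the share as measured without error, which an estimate by deconvolution would not be.

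**Reading the two steps together.** The row at zero correlation is the key condition. A shift common to all participants, or one unrelated to HRSD-24 change, leaves the correlation's error rate alone. A comparison of responders with non-responders likewise needs the cell-mix change to track response. Section 7.2 does not say whether the responder test is that comparison or a pre-post test within responders. The latter would register any systematic shift in mix.

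**The case against.** Several points on the other side are sound.

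- **Nothing in the documents shows that cell mix shifts.** A reader might infer that changed cell counts will be reported as changed pathways. The documents support only that they could be, under the conditions above.
- **The randomized contrast is partly protected.** Both Study 1 arms receive ten isoflurane sessions with the same induction and fluids (section 5.1), so shifts due to time or anesthesia in general should balance on average. A reader might infer that the High versus Low comparison is invalid. It is not: the difference in blood RNA remains a valid treatment contrast, and only its attribution to changes inside cells is open. This protection does not extend to the responder test, the HRSD-24 correlation or open-label Aim 5.
- **Composition is measured after treatment.** A treatment-caused shift in leukocyte mix may itself be an immune finding, so requiring every candidate to survive adjustment would discard real results.
- **The plan leaves much unspecified.** Sample preparation is not described, so mixed-cell RNA is an inference. Normalisation is unspecified, so the text does not establish that raw values are analysed. No multiplicity rule is given, so nothing can be said about signals surviving one. The named targets include IL-10 and other cytokines but also ion-channel and other genes, so they cannot be called mostly immune.
- **The aims are exploratory**, and the adjustment could be added later from the same data.

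These points limit the claim and shape the remedy. They do not supply the missing analysis: as written, 7.2 cannot separate a composition shift from a within-cell change.

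**Conclusion.** The concern holds in conditional form. Section 7.2 takes no account of leukocyte composition. If the RNA is from mixed cells, and if change in mix is caused by treatment or associated with response or HRSD-24 change, composition shifts could be misread as within-cell pathway changes. If there is no such association, the error rate of the correlation is unaffected.

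The size is unknown. The level shifts and rejection rates above rest entirely on assumed cell shares, enrichment and noise. They show that a material effect is possible, not that it is expected. This is an inexpensive improvement to exploratory aims, with no bearing on the Aim 1 comparison.

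**What to change.** In section 7.2, prespecify the following:

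1. Estimate one or two main leukocyte fractions in each sample by deconvolution of the same RNA-Seq data.
2. Repeat the responder, between-arm and HRSD-24 analyses in a regression model with change in those fractions as covariates.
3. Report unadjusted and adjusted results side by side.
4. Report any change in the fractions as a result in its own right.
5. Limit claims of within-cell pathway change to signals that persist after adjustment. Signals seen only without adjustment stay reportable as changes in blood RNA.

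No extra blood or participant burden is needed. The costs are additional analysis, probably fewer within-cell claims, and one or two degrees of freedom: for the correlation at n = 30, from 30 − 2 = 28 to 27 or 26. The sample does not support adjusting for many fractions. Estimated fractions are imprecise and partly derived from the genes under test, so adjustment may be incomplete and the report should say so.
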